8.2. Secondary Efficacy Analysis

The iADRS, MMSE, NPI-10, and ZBI, in the ITT analysis set, and the ADAS-Cog12, ADCS-ADL, iADRS, MMSE, NPI-10, and ZBI, in the ITT-mild analysis set will be analyzed using the MMRM model as described for the primary analysis, with the exception for MMSE where the baseline value for the endpoint being analyzed is the MMSE baseline; therefore, the model for MMSE will include the categorical fixed effects of treatment group, Visit, and pooled site, along with the continuous, fixed covariate of baseline MMSE score and the interactions of treatment group and baseline MMSE with Visit.

The CDR-SB is only collected at Screening and Week 52. Therefore, the CDR-SB will be analyzed using ANCOVA with a model that includes treatment group, pooled site, and baseline MMSE. Plasma biomarkers will be analyzed with the MMRM analysis as described above.

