11.3.2 Secondary Analyses

The iADRS^{18,19} is a linear combination of scores from two well-established, widely accepted, therapeutically sensitive measures of AD: the ADAS-Cog and ADCS-iADL (the instrumental component of the ADCS-ADL). The iADRS has been validated and statistical properties of the composite performance have been described²⁰. All items of the ADAS-Cog12 and the ADCS-iADL will be included to generate this primary efficacy composite measurement without additional weighting.

Secondary clinical endpoint data (iADRS, NPI, MMSE, and ZBI) measured repeatedly will be analyzed using the same types of linear mixed models as described for the primary analysis.

Plasma assays may include P-tau181 and/or P-tau217, SavaDx and neurofilament light chain, and additional plasma biomarkers may be measured. All plasma biomarker data involving repeated measures will also be analyzed using the same types of linear mixed models as described for the primary analysis.

CDR-SB data will be analyzed using ANCOVA models with treatment group as a factor and the baseline value as a covariate.

All secondary analyses will be conducted using two-sided tests at the alpha = 0.05 level of significance, with no adjustments for multiplicity.

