3.2.1.2. Secondary Efficacy Endpoint(s) and Estimand(s)

The secondary efficacy endpoints of this study include the following:

- Mean change in the ADAS-Cog12 from baseline to Weeks 4, 16, 28 and 40
- Mean change in ADCS-ADL from baseline to Weeks 4, 16, 28 and 40
- Mean change in the iADRS (range 0 – 139, lower score indicates greater impairment) from baseline to Weeks 4, 16, 28, 40 and 52
- Mean change in the NPI-10 (range 0 – 120, higher score indicates greater impairment) from baseline to Weeks 28 and 52
- Mean change in the MMSE (range 0 – 30, lower score indicates greater impairment) from the screening visit to Weeks 28 and 52
- Mean change in the CDR-SB (range 0 – 18, higher score indicates greater impairment) from the screening visit to Week 52
- Mean change in the ZBI (range 0 – 88, higher score indicates greater caregiver burden) from baseline to Weeks 4, 16, 28, 40 and 52.

The estimands for the secondary efficacy endpoint(s) are similar to the co-primary estimands. Each secondary estimand has the following components:

Population	Participants with mild-to-moderate AD dementia who meet the study's inclusion and exclusion criteria.
Treatments	Simufilam 100 mg twice daily or placebo
Endpoints	ADAS-Cog12, ADCS-ADL, iADRS, NPI-10, MMSE, CDR-SB, ZBI
Summary Measure	Difference between treatments in LS mean change from baseline to the time points designated above
Intercurrent Events	All deviations from the intended dosing regimens and use of concomitant events medications will be handled consistently using a treatment policy strategy. Early study discontinuation will be consistently accounted for using a hypothetical strategy to estimate what would have been observed if the participant had not discontinued.

In addition, secondary estimands include the primary and secondary endpoints assessed in the population of participants with stage 4 AD. Stage 4 (mild) is defined as participants with baseline MMSE 21-27. Stage 4 and 5 represent all randomized participants.

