6.1.3. Multiple Comparisons

The co-primary endpoints of ADAS-Cog12, and ADCS-ADL will each be tested at $p=0.05$ using the ITT analysis set. Multiplicity among secondary endpoints in the ITT analysis set will be controlled using a hierarchical, gatekeeping strategy. Secondary endpoints will be tested in the following order: iADRS, CDR-SB, ZBI, MMSE, and NPI-10. Testing will proceed in this order

until the first non-significant p value ($p > 0.05$). The first endpoint with $p > 0.05$ and all subsequent endpoints in the order will be declared non-significant, and all endpoints preceding the first non-significant test will be declared significant.

For the set of significant endpoints in the ITT analysis set, the corresponding endpoints in the mild subgroup (ITT-mild analysis set) will be tested. Testing for the mild cohort will proceed in the same order as for the secondary endpoints referenced above until the first non-significant p value. The first endpoint with $p > 0.05$ and all subsequent endpoints in the order will be declared non-significant, and all endpoints preceding the first non-significant test will be declared significant.

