6.1.4. Handling of Dropouts or Missing Data

Although every attempt will be made to ensure participants remain in the study to completion and all data is collected as scheduled, the occurrence of missing data cannot be completely prevented.

An incomplete start or stop date of an AE or a medication will be imputed as described in section 6.1.8.

Any participant who withdraws from the study will be considered to have missing data at all subsequent visits. The primary analytic approach for efficacy assumes missing at random (MAR) to estimate what would have been observed if the participant had not discontinued. A reference-based multiple imputation sensitivity analysis (copy reference) will be employed in which missing not at random is assumed such that after discontinuation, drug-treated participants will have placebo-like values imputed for their missing data.

If up to two individual items of the total 12 items for the ADAS-Cog12 (maximum score = 80) are missing for non-cognitive reasons, the total score will be imputed by multiplying the observed score (i.e. the score for the non-missing items) by a factor that includes the maximum scores for the missing item(s) as follows:

$$\text{Imputed score} = \text{Observed score} * (80/[80-\text{maximum score for missing items}]).$$

As an example, if the first item “Word Recall” (maximum score = 10) and the second item “Commands” (maximum score = 5) are missing, the observed score will be multiplied by the factor $80/(80-[10+5])$ or $80/65$ or 1.23. The imputed score will be rounded to the nearest integer. ADAS-Cog12 tests with more than two missing items will be considered missing scores.

Missing items on other assessments will not be imputed; such scores will be considered missing.

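### The CDR-SB analysis has no missing-data step, so dropouts' observed decline on other scales cannot inform the outcome its estimand asks for

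*SAP*

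**What the plan says.** SAP 6.1.3 fixes the order: "Secondary endpoints will be tested in the following order: iADRS, CDR-SB, ZBI, MMSE, and NPI-10". A non-significant CDR-SB stops ZBI, MMSE and NPI-10. Only endpoints significant in the ITT set are then tested in ITT-mild.

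SAP 3.2.1.2 lists CDR-SB, as change from screening to Week 52, among the endpoints of the secondary estimand. It adds: "Early study discontinuation will be consistently accounted for using a hypothetical strategy to estimate what would have been observed if the participant had not discontinued".

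SAP 8.2 specifies: "The CDR-SB is only collected at Screening and Week 52. Therefore, the CDR-SB will be analyzed using ANCOVA", with terms for treatment, pooled site and baseline MMSE. Protocol 11.3.2 also names ANCOVA: "CDR-SB data will be analyzed using ANCOVA models with treatment group as a factor and the baseline value as a covariate". Neither describes any handling of a missing Week 52 value.

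SAP 6.1.4 treats all visits after withdrawal as missing and takes MAR as the main efficacy assumption. SAP 8.1 explains MAR as allowing dropout to depend on observed outcomes and covariates. Multiple imputation (8.1.1) is confined to the co-primary endpoints.

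CDR is also collected at early termination (Protocol 7.1.6 and 9). SAP 4.2 maps early-termination data to visit windows for both safety and efficacy.

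**The concern.** For most of the other scales, the repeated-measures model carries the hypothetical strategy: a dropout's earlier visits inform the Week 52 estimate. CDR-SB has a single scheduled post-baseline assessment, so ANCOVA has no earlier visit to draw on. A participant with no Week 52 value leaves the model, even when ADAS-Cog12 and ADCS-ADL up to Week 40 and MMSE at Week 28 show how fast that person was declining.

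The ANCOVA therefore needs dropout to be unrelated to decline given arm, pooled site and baseline MMSE. That is a stronger condition than MAR as SAP 8.1 describes it. If the condition fails differently in the two arms, the CDR-SB comparison is biased. Provided iADRS has succeeded, the CDR-SB result also decides whether three further endpoints, and the matching ITT-mild tests, are reached.

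**Working it through.** **The plan's own figure.** SAP 2.2 gives the only power calculation, for ADAS-Cog: a 45% difference on a placebo change of 5.0 (2.25 points), SD 8.5, two-sided 0.05, 90% power. n = 2 × (1.960 + 1.282)² × 8.5² / 2.25² ≈ 300 per arm, and 300/0.80 = 375. Both reproduce. There is no power figure or SD for CDR-SB. Only the 20% dropout and the 804 randomized carry over.

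**Participants affected.** 804 × 0.20 ≈ 161, leaving about 643, or 322 per arm. At 10% to 30% dropout, 80 to 241 are affected. These counts assume no early-termination CDR-SB is used as Week 52.

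**Early-termination values.** The Week 52 window in SAP Table 2.1 is Day 324 to Day 407, so a CDR-SB from Day 324 would map to Week 52. For earlier values the text is open. The rule dropping an assessment that falls in a window where it is not scheduled sits in the safety paragraphs of 6.1.5. The efficacy paragraph says only nearest scheduled visit. On one reading the early value is discarded. On the other it stands in for Week 52. Neither estimates what would have been seen without discontinuation.

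**Size of bias.** Let ρ be the correlation of Week 52 CDR-SB change with an interim score, r the correlation of dropout propensity with that score, and d the dropout rate. ρ and r are assumptions, to be read as conditional on the ANCOVA covariates. In an arm where dropout follows the score, completers look better by

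bias (SD) = ρ × r × φ(z₁₋d) / (1 − d).

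At d = 0.20, z = 0.842, φ = 0.280 and φ/(1 − d) = 0.350. With r = 0.5 this is 0.175ρ. The SE of the difference is √(2/321.6) = 0.079 SD.

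Mechanism in one arm only, no true effect:

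| ρ | Bias (SD) | Two-sided rejection, completers only | Rejection, MAR using the interim score |
|---|---|---|---|
| 0.3 | 0.05 | about 10% | 4.7% to 4.9% |
| 0.5 | 0.09 | about 20% | 4.4% to 5.3% |
| 0.7 | 0.12 | about 34% | 4.6% to 5.2% |

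The last column comes from 4,000 simulated trials per setting. Those trials also reproduced the completer-only results, at 9% to 10%, 20% to 21% and 34% to 35%. Over d = 10% to 30% and ρ and r each 0.3 to 0.7, the formula gives 0.02 to 0.24 SD.

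**Direction.** If placebo loses its decliners, placebo completers look better and the error goes against simufilam. At ρ = 0.5, bias/SE = 0.0875/0.0789 = 1.11, so about 19.7% of trials reject against simufilam and about 0.1% in its favour. If the active arm loses its decliners, the sign reverses. With a true benefit of 0.2 SD, the MAR estimator rejects in 72% to 76% of trials in either case. Completer-only rejection falls to 47%, 31% and 17% (ρ = 0.3, 0.5, 0.7) in the placebo case and rises to 90%, 95% and 99% in the active case.

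**Same mechanism in both arms, or dropout unrelated to the score.** Bias is about zero and rejection 5.0% to 5.7%. A separate simulation with equal mechanisms (402 per arm, 20% to 21% dropout, assumed CDR-SB change SD 2.7, correlation 0.6 to 0.67 with ADAS-Cog12 change) gave SE 0.210 for completers and 0.205 with imputation, a gain of about 2%.

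**The case against.** Single-time-point ANCOVA is itself valid under MAR given its covariates, and it is the protocol's stated method in a study run under a Special Protocol Assessment. No analysis in the SAP borrows across scales. MMSE and NPI-10 have only Week 28 before Week 52, so someone who leaves before then, with no mapped early-termination score, adds no post-baseline value to those models either. Nothing in the documents suggests that dropout follows decline in one arm and not the other. Imputation also wins partly by construction here, because simulated dropout depends on a score that the imputation uses. The CDR-SB result matters only once iADRS is significant, and the co-primaries are untouched.

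All of this stands, and it makes the point an improvement rather than the correction of an error. It does not remove the gap: the estimand asks for the outcome without discontinuation, and observed data bearing on that outcome are not used.

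A reader might also infer that interim CDR-SB data are being discarded. None are scheduled; the unused scores are on other scales. Nor do the documents say that every dropout is deleted, since late early-termination values may count as Week 52.

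**Conclusion.** The point holds as a cheap improvement. The CDR-SB estimator rests on a stronger dropout assumption than the repeated-measures analyses, for an endpoint placed second in the gated order, and about 161 of 804 participants could be affected at 20% dropout.

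The bias is a possibility, not a finding: about zero if dropout relates to decline alike in both arms, and roughly 0.05 to 0.12 SD if it does so in one arm only, at 20% dropout with r = 0.5 and ρ from 0.3 to 0.7. The correlations and the one-arm mechanism are assumptions with no source in the documents.

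A reader might take the 10% to 34% rejection rates as inflated false positives in favour of simufilam. The documents do not support that: the direction depends on which arm loses its decliners, and in the placebo case nearly all the excess goes against the drug.

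**What to change.** Before unblinding, amend SAP 8.2 as follows:

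- Impute missing Week 52 CDR-SB under MAR from treatment, baseline CDR-SB, baseline MMSE and the observed post-baseline ADAS-Cog12, ADCS-ADL and MMSE scores.
- Fit the ANCOVA to each completed data set and combine with Rubin's rules.
- Repeat in ITT-mild, where a CDR-SB table (14.2.6.2) is already planned.
- Keep the completer ANCOVA as supportive.
- State that an early-termination CDR-SB taken before the Week 52 window is not used as the Week 52 value.

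The cost is new programming and reliance on an imputation model. The code in 8.1.1 cannot simply be reused: it imputes one endpoint from its own visits under a placebo-based copy-reference assumption, so it must be adapted to MAR and several scales. No extra data are needed, and ANCOVA remains the analysis model.

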6.1. Statistical Definitions and Algorithms

6.1.1. Baseline

The last observation recorded on or before the first dose of treatment will be used as the baseline observation for all calculations of change from baseline. In most cases, this will be the baseline visit (Day 1) pre-dose observation. In some cases, however, the baseline values may be obtained from the 60-day screening phase. For example, because MMSE is taken at screening but not at the baseline visit, the MMSE value obtained at screening will be used as the baseline value.

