6.1.2. Adjustments for Covariates

Efficacy analyses will include as covariates the baseline value of the endpoint being analyzed and the MMSE baseline score, along with the interaction of these covariates with Visit. Investigative site (pooled, see section 6.1.6) will also be included as a categorical fixed effect.

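### SAP 8.2 leaves baseline CDR-SB out of the CDR-SB ANCOVA, against protocol 11.3.2 and SAP 6.1.2, so the second test in the secondary sequence has two possible models

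*SAP*

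**What the plan says.** SAP 8.2, having noted that CDR-SB is measured only at screening and Week 52, says: "the CDR-SB will be analyzed using ANCOVA with a model that includes treatment group, pooled site, and baseline MMSE". Protocol 11.3.2 has a different model: "CDR-SB data will be analyzed using ANCOVA models with treatment group as a factor and the baseline value as a covariate". SAP 6.1.2 sets a general rule: "Efficacy analyses will include as covariates the baseline value of the endpoint being analyzed and the MMSE baseline score", with pooled site as a further fixed effect. It makes no exception for CDR-SB.

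Section 8.2 does state one departure from that rule and explains it: "with the exception for MMSE where the baseline value for the endpoint being analyzed is the MMSE baseline". Nothing similar is said for CDR-SB.

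A baseline CDR-SB exists. The schedule of activities has CDR at screening, SAP 3.2.1.2 defines the endpoint as change from screening to Week 52, and SAP 6.1.1 allows for this: "In some cases, however, the baseline values may be obtained from the 60-day screening phase".

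On testing, SAP 6.1.3 says: "Secondary endpoints will be tested in the following order: iADRS, CDR-SB, ZBI, MMSE, and NPI-10". It stops at the first result above 0.05, and then: "For the set of significant endpoints in the ITT analysis set, the corresponding endpoints in the mild subgroup (ITT-mild analysis set) will be tested". SAP Section 10 declares no change from the planned analysis.

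**The concern.** Read together with 6.1.2, the CDR-SB model contains baseline CDR-SB. Read as the complete list that 8.2 appears to give, it does not. The protocol's own model (treatment and baseline CDR-SB only) is a third specification. A confirmatory test in a fixed sequence needs one model, settled before the data are seen.

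On the second reading the outcome is a change score with no adjustment for its own baseline, which fixes the slope of Week 52 CDR-SB on baseline CDR-SB at 1 instead of estimating it. If the true slope is below 1, the residual variance is larger than it need be, and a chance imbalance in baseline CDR-SB is over-corrected. These are two views of much the same loss.

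The stake is the sequence. If iADRS is significant and CDR-SB then misses, ZBI, MMSE and NPI-10 are all declared non-significant, and neither CDR-SB nor those three endpoints is tested in ITT-mild.

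**Working it through.** **The plan's own figure.** The only power calculation is for ADAS-Cog (SAP 2.2): difference 0.45 × 5.0 = 2.25, SD 8.5, 90% power, two-sided 0.05. Then n = 2 × (1.960 + 1.282)² × 8.5² / 2.25² = 300 per group, and 300 / 0.8 = 375. Both figures reproduce, but they say nothing about CDR-SB.

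**Assumed inputs.** Let B be screening CDR-SB, Y Week 52 CDR-SB, M baseline MMSE and D = Y − B. Scale B and M to variance 1. None of the following is in the documents:
- k = SD(Y)/SD(B): 1.0 or 1.25
- ρ = corr(B, Y): 0.6, 0.7, 0.8
- corr(M, B): −0.5
- c = corr(M, Y): −0.3, −0.4, −0.5

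**Formulas.**
- Without B: Var(D | M) = 1 + k² − 2ρk − (ck + 0.5)²
- Slope of Y on B given M: β = (ρk + 0.5ck) / 0.75
- With B: Var(D | M, B) = k²(1 − c²) − 0.75β²
- Variance ratio VR = Var(D | M) / Var(D | M, B)

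**One cell in full** (k = 1, ρ = 0.7, c = −0.4):
- Var(D | M) = 2 − 1.4 − 0.1² = 0.59
- β = (0.7 − 0.2) / 0.75 = 0.667
- Var(D | M, B) = 0.84 − 0.75 × 0.444 = 0.507
- VR = 0.59 / 0.507 = 1.16

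**All 18 cells**, VR with β in brackets:

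| k | ρ | c = −0.3 | c = −0.4 | c = −0.5 |
|---|---|---|---|---|
| 1.0 | 0.6 | 1.19 (0.60) | 1.26 (0.53) | 1.36 (0.47) |
| 1.0 | 0.7 | 1.11 (0.73) | 1.16 (0.67) | 1.25 (0.60) |
| 1.0 | 0.8 | 1.04 (0.87) | 1.08 (0.80) | 1.15 (0.73) |
| 1.25 | 0.6 | 1.05 (0.75) | 1.09 (0.67) | 1.14 (0.58) |
| 1.25 | 0.7 | 1.01 (0.92) | 1.03 (0.83) | 1.06 (0.75) |
| 1.25 | 0.8 | 1.01 (1.08) | 1.00 (1.00) | 1.01 (0.92) |

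The range is 1.00 to 1.36 and the median 1.084 (1.164 at k = 1.0, 1.026 at k = 1.25). The slope is below 1 in 16 of 18 cells. Moving corr(M, B) from −0.3 to −0.7 moves the median from 1.14 to 1.03 and the maximum from 1.44 to 1.29.

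**In participants.** With 804 randomised (SAP 2.2), the planned 20% dropout and an equal split, 804 × 0.8 / 2 = 321.6 per arm. At the median, 321.6 / 1.084 = 297.

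**In power.** If the model with baseline CDR-SB had 90% power, the model without it has Φ((1.960 + 1.282)/√VR − 1.960):
- VR 1.026: 89.2%
- VR 1.164: 85.2%
- VR 1.36: about 79%

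In terms of the partial correlation r between change and baseline, VR = 1/(1 − r²). So r = 0.2 gives VR 1.042 and 88.8%, and r = 0.3 gives VR 1.099 and 87.1%.

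**Type I error and imbalance.** In 2,000 simulated null trials in each of four settings (322 per arm, stratified by MMSE, 40 site effects, no dropout), the rejection rate was 4.5 to 5.4% without baseline CDR-SB and 4.5 to 5.1% with it. Per unit of chance baseline imbalance, the treatment estimate moved by −0.44, −0.34, −0.22 and −0.08 without the covariate, and by 0.03 to −0.06 with it.

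**Does the choice change the verdict?** In 3,000 simulated trials per setting (300 per arm, k = 1.3, corr(M, B) = −0.5, ρ from 0.6 to 0.9, no site effects), the two SAP readings disagreed on significance in 0.2 to 2.5% of null trials and in 0.4 to 4.6% of trials at 90% power. Taking the better of the two gave a type I error of about 4.8 to 6.7%.

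**The case against.** The SAP can be read without conflict. Section 8.2 says what the model includes, not that nothing else enters; 6.1.2 is a general rule; and where the SAP drops a baseline term (MMSE in 8.2, the subgroup models in 8.4) it says so. On that reading the silence on CDR-SB means that 6.1.2 applies. This is a fair reading, but not the only one: 8.2 repeats pooled site and baseline MMSE, both already in 6.1.2, and omits only the endpoint's own baseline. The two-visit schedule explains ANCOVA in place of the repeated-measures model, not the missing covariate.

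The harm is also conditional. It needs the shorter model to be fitted, iADRS to be significant, and a CDR-SB p-value that crosses 0.05 because of the omission. The rates of disagreement above are small. The magnitude has no CDR-SB input from the documents, and a median over equally weighted chosen cells is an illustration, not an estimate. All of this stands and limits the size of the point, but it does not settle which model is planned.

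Two side points carry less weight. The CDR-SB sentence in 8.2 names no analysis set, but 6.1.3 and planned Tables 14.2.6.1 (ITT) and 14.2.6.2 (ITT-mild) make the sets clear. Pooled site and baseline MMSE are also added to the protocol's other efficacy models, so the silence of Section 10 is not peculiar to CDR-SB.

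**Conclusion.** The point holds. As listed, the CDR-SB model in SAP 8.2 drops the protocol's only covariate and departs from SAP 6.1.2 without a reason, at the second step of the secondary sequence. The textual finding is firm and does not depend on the calculations.

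The numerical cost applies only if the 8.2 list is complete, and it rests wholly on assumed correlations and SD ratios: residual variance multiplied by 1.00 to 1.36, more at an SD ratio of 1.0 than at 1.25, and possibly no loss at all. A single model fixed in advance keeps type I error near 5%; an open choice between models need not. The co-primary analyses are unaffected. This should be corrected, but it does not threaten the trial's main conclusion.

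**What to change.** Before unblinding, replace the CDR-SB model sentence in SAP 8.2 with, for example: *Change in CDR-SB from screening to Week 52 will be analysed by ANCOVA with treatment group, pooled site, screening CDR-SB and baseline MMSE, in the ITT and ITT-mild analysis sets.* This satisfies 6.1.2 and restores the protocol's covariate.

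In Section 10, record that pooled site and baseline MMSE are added to the protocol's CDR-SB model; the same entry can cover the other efficacy models to which these terms were added. If baseline CDR-SB was left out on purpose, give the reason in 8.2 and list the exception in 6.1.2 and Section 10.

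The cost is one phrase in 8.2 and one line in Section 10. The screening CDR is already collected, and the model uses one more degree of freedom.
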